## Rationale for Addendum

The Clinical Investigation Plan (CIP) Version 1.0 states that data will only be captured for 2 hours post apheresis procedure. Additional data capture of safety information through 24 hours post transfusion has been requested. This addendum describes the analysis of the additional safety data.

Other notable modifications include:

- Analyses requested post database lock (from the original database) are now documented
- Analyses requested for additional safety discussion to be included in the Clinical Investigation Report

## 1. INTRODUCTION

The original analysis was described in the final version of the Statistical Analysis Plan Version 1.0 (11-Nov-2014). Subsequent to the original database lock (17-Apr-2015), additional analyses were requested in an ad hoc manner to support the Clinical Investigation Report (CIR). More recently, additional data were requested to include safety information through 24 hours post procedure rather than 2 hours as originally captured.

This document describes the statistical analysis methods and data presentations to be used in the summary and analysis of the 24 hour safety data from Study CTS-5043. Related documents are the study protocol, case report forms, and original Statistical Analysis Plan (SAP).

All analyses will be conducted using SAS version 9.4 or higher.

### 1.1 Changes from original SAP Prior to Amendment

Subsequent to the initial database lock, the following tables and listings were requested in an ad hoc manner.

A WBCD procedure summary of specific parameters of interest were summarized. In particular:

- Platelets (pre and post procedure)
- Percent change in platelets
- WBCs (pre procedure)
- Whole blood processed
- Total blood volume processed
- Procedure duration
- Total waste bag volume
- Average whole blood flow

The following additional data listings were also provided:

- Blood products transfused
- Anticoagulants
- Replacement fluids
- Waste bag CBC
- Pre and Post procedure lab counts

Analyses by various subgroups were also requested. The first subgroup was defined as procedures that used an anti-coagulate containing hydroxyethyl starch (HES). It was noted that HES was used for most of the procedures at Site 3, and never at the other sites. Thus, the existing presentations provide information about procedures that used HES.

An additional subgroup analysis was requested to assess the potential impact of the use of blood warmers during the apheresis procedure. Blood warmers were exclusively used at Site 1. The existing presentations provide information about the use of blood warmers.

## 2. SOURCE DATA

The original data capture system was Open Clinica with data management provided by Terumo BCT. As noted earlier, safety data were only collected through 2 hours post procedure. This data management system was retired shortly after database lock so it was not available for collection of additional safety data.

The additional safety data collected primarily consist of laboratory data and adverse event data through 24 hours post procedure. To further support a safety discussion in the CIR, additional data for blood products transfused will also be collected.

A new EDC system (Merge) was established, which contains much of the original data as well as the additional data. The following CRF pages were implanted into Merge:

- Adverse event
- Apheresis procedure (date, time, duration)
- Blood products transfused
- Laboratory data
- Medical history
- Concomitant medications

All analyses related to these CRF pages will be based solely on the new EDC. Some CRF pages from the original database were not expected to contribute to the additional safety information. Thus, analyses with respect to those CRF pages will continue to use data from Open Clinica. These CRF pages are:

- Demographics
- Vital signs
- Procedure Information (other than date, time, duration)
- Replacement fluids
- Device deficiencies

The additional safety data will only be collected at Sites 1 and 3. While Site 2 is not participating in the additional safety data collection, the corresponding data will be included in the Merge system in order to have a single database with key CRF pages. This avoids the situation where data from the same CRF come from different sources.

## 3. EFFICACY ANALYSES

No new efficacy analyses will be performed. However, given additional laboratory data are collected, the efficacy analysis data will need to be re-created using the new EDC data. The newly created efficacy analysis data will be compared to the original to identify any potential changes.

During the collection of additional data, it is possible to have multiple records for a particular lab for the same timepoint (pre-procedure, within 2 hours post procedure, 2-24 hours post procedure). Due to database limitations, repeat tests are flagged using the character lab result field. Any value that is a repeat lab draw within the same timepoint will have a “Dx” in the field, where “x” is the repeat draw number. For the analysis of the primary and secondary

endpoint, the record with the largest WBC count will be used if there are multiple draws in the within 2 hours post procedure window. For supportive analysis of HCT and Platelets, the last draw will be used for analysis.

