### **4.0 PUBLISHED CLINICAL EXPERIENCE**

Routine use data have been summarized in a published manuscript in Vox Sanguinis December 2012 [13]. Given the paucity of patients in need of leucodepletions and marked differences in clinical presentation as well as blast properties (e.g., size, density), formal clinical trials comparing leucodepletion technologies have never been executed.

This study compared the results of the WBC depletion protocols from the Spectra Optia System with that of the COBE Spectra System. An evaluation was conducted of 8 leukodepletions performed with the Spectra Optia System in AML patients with clinical signs of leukostasis between November 2011 and July 2012, and from 15 leukodepletions performed with the COBE Spectra System between June 2010 and October 2011.

Patients did not differ with respect to epidemiological data. However, the pre-apheresis leukocyte count (WBC) was significantly higher in Spectra Optia IDL patients. The indication for leukodepletion was patients with AML with clinical evidence of leukostasis. Tolerability was excellent with both devices. Basic apheresis denominators such as duration, processed volume, inlet pump rate, ACD-A consumption and product volume were similar. A negative correlation between pre-apheresis WBC and collection efficiency was noted. Mean collection efficiency for leukocytes with Spectra Optia IDL (47.3%) was similar to that with COBE Spectra MNC (50.5%). Platelet attrition was similar with both devices, approximately 30%.

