## 10.3 During/Post each Spectra Optia Apheresis Procedure

1. Procedure Data from Site Source Documents
  - a. Date, time of apheresis
  - b. Anticoagulant(s) and volume(s)
  - c. Replacement fluid volumes and solution(s) (not administered via Optia)
  - d. Apheresis product volume (mL), if available
2. Procedure Data from Spectra Optia Data Logs
  - a. Date, time of apheresis
  - b. Duration of apheresis procedure
  - c. Inlet to AC ratio
  - d. AC infusion rate
  - e. Average inlet flow (mL/min)
  - f. Average collect flow (mL/min)
  - g. Waste bag (depletion product) volume (mL)
  - h. Whole blood processed (mL)
  - i. Fluid balancee (%)
  - j. Replacement fluid volume(s) and solution(s) (administered via Optia)
3. The following laboratory results from the cellular depletion product (waste bag), if available
  - a. CBC (WBC, PLT count, hematocrit, and RBC count)
  - b. Collected cellular depletion product (waste bag) volume
4. The following laboratory results, including collection dates/times, from the patient during and for 2 hours following apheresis, if available.
  - a. CBC (WBC, PLT count, hematocrit, and RBC count)
  - b. Coagulation: PT, INR
  - c. Calcium (ionized and total)
5. Record blood products, medications, and fluids (beyond those mentioned above) administered during and for 2 hours following apheresis.
6. Record all adverse events (AEs) and serious adverse events (SAEs) during the apheresis procedure and for 2 hours post procedure.

7. Record device deficiencies or malfunctions.

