### **2.4 Data for Collection**

Clinical routine-use data have been collected retrospectively, between November 2011 and December 2013, from centers experienced with the Spectra Optia System's WBCD procedure.

With this amendment, additional safety data will be collected for the 22-hour time period from 2 hours postapheresis until 24 hours postapheresis.

Specifically, the following new data will be collected:

1. Adverse event data for AEs that occurred during the 24-hour time period following the WBCD procedure (eg, date/time of start and end, ongoing, severity, action taken relationship to device/apheresis procedure/underlying disease/treatment for underlying disease, outcome, SAE, unexpected adverse device effect).

Note: The Investigator at each site will document his/her opinion of the relationship of the event to the procedures or underlying disease. The criteria below, in addition to good clinical judgment, should be used in determining relatedness.

Not Related: The event is clearly related to factors other than the study device and/or procedure(s), such as the subject's clinical state.

Possibly Related: The event follows a reasonable temporal sequence from the time of study treatment administration/ procedure, and/or follows a known response pattern to study device/procedure(s) but could have been produced by other factors, such as the subject's clinical state or other therapeutic interventions.

Probably Related: The event follows a reasonable temporal sequence from the time of study device/procedure(s) and cannot be reasonably explained by other factors, such as the subject's clinical state or therapeutic interventions.

Definitely Related: The event follows a reasonable temporal sequence from the time of study device/procedure(s), and follows a known response pattern, and cannot be reasonably explained by other factors. In addition, the event occurs immediately following study procedure(s), and/or improves on stopping the study procedure, and/or reappears on resumption of study procedure(s).

2. Blood products transfused during the 24-hour time period following the WBCD procedure (eg, reason [AE or underlying disease], blood product, number of units, date/time of start and end).
3. Postapheresis clinical laboratory results, as available (eg, prothrombin time [PT], international normalized ratio [INR], WBC count, platelet count, hematocrit, red blood cell count).

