## **7. APPENDICES**

### **Appendix 1. Tables, Listings, and Figures**

## Appendix 1. Tables, Listings, and Figures

Table of Contents:

Table 14.1.1	Disposition	All Subjects and All Procedures
Table 14.1.2	Demographics and Baseline Characteristics	Safety Analysis Set
Table 14.2.1.1	Percent Decrease in WBC	Full Analysis Set
Figure 14.2.1.1	Percent Decrease in WBC	Full Analysis Set
Table 14.2.1.2	Percent Decrease in WBC	Per-Protocol Set
Figure 14.2.1.2	Percent Decrease in WBC	Per-Protocol Set
Table 14.2.2.1	Percent Processed WBC (CE1)	Full Analysis Set
Figure 14.2.2.1	Percent Processed WBC (CE1)	Full Analysis Set
Table 14.2.2.2	Percent Processed WBC (CE1)	Per-Protocol Set
Figure 14.2.2.2	Percent Processed WBC (CE1)	Per-Protocol Set
Table 14.2.3	WBCD Procedure Summary	Full Analysis Set
Table 14.3.2	Summary of HCT	Full Analysis Set
Table 14.3.1.1.1	Overview of Treatment Emergent Adverse Events	Safety Analysis Set – 2 Hour Monitoring
Table 14.3.1.1.2	Overview of Treatment Emergent Adverse Events	Safety Analysis Set – 24 Hour Monitoring
Table 14.3.1.2.1	Treatment Emergent Adverse Events by SOC and PT	Safety Analysis Set – 2 Hour Monitoring
Table 14.3.1.2.2	Treatment Emergent Adverse Events by SOC and PT	Safety Analysis Set – 24 Hour Monitoring
Table 14.3.1.3.1	Treatment Emergent Adverse Events by Severity	Safety Analysis Set – 2 Hour Monitoring
Table 14.3.1.3.2	Treatment Emergent Adverse Events by Severity	Safety Analysis Set – 24 Hour Monitoring
Table 14.3.1.4	Treatment Emergent Adverse Events Leading to Discontinuation of Study Procedures	Safety Analysis Set – 2 Hour Monitoring
Table 14.3.1.5.1	Serious Treatment Emergent Adverse Events by SOC and PT	Safety Analysis Set – 2 Hour Monitoring
Table 14.3.1.5.2	Serious Treatment Emergent Adverse Events by SOC and PT	Safety Analysis Set – 24 Hour Monitoring
Table 14.3.1.6.1	Treatment Emergent Adverse Events Related to Study Device	Safety Analysis Set – 2 Hour Monitoring
Table 14.3.1.6.2	Treatment Emergent Adverse Events Related to Study Device	Safety Analysis Set – 24 Hour Monitoring
Table 14.3.1.7.1	Treatment Emergent Adverse Events Related to Study Procedure	Safety Analysis Set – 2 Hour Monitoring
Table 14.3.1.7.2	Treatment Emergent Adverse Events Related to Study Procedure	Safety Analysis Set – 24 Hour Monitoring

Table 14.3.1.8.1	Treatment Emergent Adverse Events Related to Underlying Disease	Safety Analysis Set – 2 Hour Monitoring

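### The last-draw rule for platelets and HCT carries no transfusion condition, so it can understate platelet and red-cell loss where a procedure has repeat post-procedure draws

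*SAP*

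**What the plan says.** SAP section 3 anticipates more than one laboratory record within a timepoint: before the procedure, in the first 2 hours after it, or from 2 to 24 hours after it. For the WBC endpoints, "the record with the largest WBC count will be used if there are multiple draws in the within 2 hours post procedure window". For the other two counts, "For supportive analysis of HCT and Platelets, the last draw will be used for analysis". The second rule names no window and has no transfusion condition.

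Two tabulated outputs depend on it. SAP section 1.1 adds "Percent change in platelets" to the procedure summary, which Appendix 1 lists as Table 14.2.3. Appendix 1 also lists a "Summary of HCT" table, numbered 14.3.2 (the same number is used for the transfusion summary).

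Transfusions in the relevant interval are recorded. Protocol section 10.3 asks sites to "Record blood products, medications, and fluids (beyond those mentioned above) administered during and for 2 hours following apheresis". For the 24 hours after the procedure, Amendment 1.0 section 2.4 adds the reason and "blood product, number of units, date/time of start and end". SAP section 4 uses these data in a separate summary by product and timepoint, and Appendix 1 adds a listing. Neither the rule nor the table list connects transfusion to the platelet or HCT change.

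**The concern.** Platelet loss is an unwanted effect that the protocol itself treats as worth reporting. Of the earlier two-device comparison, section 4.0 says "Platelet attrition was similar with both devices, approximately 30"%. A platelet or red-cell transfusion after the procedure raises the count. If it comes before the analysed draw, the reported change combines what the procedure removed with what the transfusion put back.

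The two rules in SAP section 3 also point in different directions. Taking the largest post-procedure WBC count gives the smallest percent decrease. It also enlarges the denominator of CE1 and so lowers that figure. The WBC rule therefore picks the value least favourable to the device. The platelet and HCT rule has no such protection: as far as transfusion is concerned, it can only move the reported loss downwards. The addendum was prompted by a regulator's request for more safety data, so a reader may look to these tables for the amount of platelet and red-cell loss.

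**Working it through.** The plan gives no figure to reproduce: the study is descriptive, with a target of at least 20 procedures (Protocol section 8.1) and no hypothesis testing (section 12.0).

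**Direction.** Let the post-procedure draws be at times t1 < t2 < ... < tk. A transfusion given before t1 was also given before tk, and one given between t1 and tk affects tk but not t1. So the last draw is never less exposed than an earlier one. If k = 1, or if no relevant transfusion falls between the draws, the rule changes nothing in this respect.

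**Size in one procedure (illustration).** The 30% loss is the figure in Protocol section 4.0. The pre-procedure count P and the transfusion increment I (both x 10^9/L) are assumptions; the documents give neither.

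Apparent loss % = 100 x [P - (0.70P + I)] / P = 30 - 100 x I/P.

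For P = 50 and I = 20: 50 x 0.70 = 35; 35 + 20 = 55; 100 x (50 - 55)/50 = -10%, a reported gain of 10%.

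**Size in the mean.** Let f be the share of procedures in which a platelet transfusion falls after an available post-procedure draw and before the last one. With the same P and I throughout:

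Mean apparent loss % = 30 - 100 x f x I/P.

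| P | I | Apparent loss, affected procedure | Mean, f = 10% | Mean, f = 25% | Mean, f = 50% |
|---|---|---|---|---|---|
| 30 | 10 | -3.3% | 26.7% | 21.7% | 13.3% |
| 30 | 20 | -36.7% | 23.3% | 13.3% | -3.3% |
| 30 | 30 | -70.0% | 20.0% | 5.0% | -20.0% |
| 50 | 10 | 10.0% | 28.0% | 25.0% | 20.0% |
| 50 | 20 | -10.0% | 26.0% | 20.0% | 10.0% |
| 50 | 30 | -30.0% | 24.0% | 15.0% | 0.0% |
| 100 | 10 | 20.0% | 29.0% | 27.5% | 25.0% |
| 100 | 20 | 10.0% | 28.0% | 25.0% | 20.0% |
| 100 | 30 | 0.0% | 27.0% | 22.5% | 15.0% |

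Negative values are reported gains. At f = 0 the mean stays at 30%. One affected procedure in 20 (f = 5%) with P = 50 and I = 20 gives 30 - 100 x 0.05 x 20/50 = 28%.

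**HCT.** Assume a 10% relative loss from an HCT of 25: 25 x 0.90 = 22.5. A rise of 1 point gives 23.5, a reported loss of 1.5/25 = 6%. A rise of 3 points gives 25.5, a reported gain of 0.5/25 = 2%.

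**After the change.** If the analysed draw precedes any post-procedure transfusion, f = 0 and the illustrative mean returns to 30%. A transfusion during the procedure affects every post-procedure draw whichever is chosen, so it needs a flag as well.

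**The case against.** The best defence is that nothing shows the rule to have any effect here. SAP section 3 says only that repeats may occur. Recording transfusions does not say how often they were given, and no passage says that repeat counts were taken to check a transfusion, or that the procedures with the greatest loss were those transfused and redrawn. A reader might infer that transfusion does mask the device's platelet loss and that the mean change is biased in its favour. The documents do not support that: they establish the direction of a possible error, not its occurrence. This part of the objection stands in full.

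A reader might also take the last draw to mean the last within 24 hours. The preceding sentence concerns the 2-hour window, and SAP section 4 plans no summary of the 24-hour laboratory data, so 2 hours is the natural reading. The text is merely not explicit.

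Other outputs also help. Waste-bag counts are collected if available and listed. They measure the cells removed, and a transfusion after the procedure does not alter them. Transfusions, pre- and post-procedure results and patients with low platelets are listed too, so about 20 procedures could be cross-checked by hand. That softens the consequence but leaves the tabulated summaries as they are.

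Finally, platelets and HCT are supportive and are not among the three outcome measures. SAP Version 1.0 is not among the documents and may hold a transfusion rule. Both points limit the weight of the concern; neither supplies a reason for preferring the last draw after the procedure.

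**Conclusion.** The point holds as a weakness in a stated rule, not as a demonstrated bias. Where there are repeat post-procedure draws, the last is at least as likely as any earlier one to follow a platelet or red-cell transfusion. Any error from that source makes the reported loss too small. This is sure as to direction, other influences between draws being equal.

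The size is unknown. On the assumed grid, the mean platelet loss reported for a 30% loss runs from 29% (P = 100, I = 10, f = 10%) to a 20% gain (P = 30, I = 30, f = 50%), and there is no effect at f = 0. These figures show sensitivity and estimate nothing about this study.

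The reach is limited to the platelet percent change in Table 14.2.3 and the HCT summary. WBC decrease and CE1 are unaffected. The change is worth making because it is cheap, and because a less exposed draw may already be in the database.

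**What to change.** In SAP section 3:

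1. State that the post-procedure rule for platelets and HCT applies to the window within 2 hours after the procedure.
2. Use the first draw after the procedure stop time that precedes any post-procedure platelet transfusion (for platelets) or red-cell transfusion (for HCT). If there is none, use the first post-procedure draw and flag the procedure.
3. Keep the last draw before the procedure as baseline.
4. Flag every procedure in which the relevant product was given between the baseline draw and the analysed draw, including during the procedure.
5. Report platelet and HCT change for all procedures, and again without the flagged ones.

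The cost is revised wording and a merge of laboratory, stop and transfusion times. The times will not be complete. Protocol section 10.3 collects draw times only if available. Transfusion start and end times are specified only for the 24 hours after the procedure, and that collection excludes Site 2. Where times are missing, a procedure can be classified only as transfused or not; the repeat-draw number described in SAP section 3 should still give the order of draws. With a target of about 20 procedures, the unflagged group will be small, so the second set of results should be read as a sensitivity check.

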#### **4. SAFETY ANALYSES**

The initial set of safety summary tables will remain as the core safety analysis and describe the safety profile from the start of the procedure through 2 hours post procedure. Additional adverse event tables will be added to summarize (cumulative) adverse events from the start of the procedure through 24 hours post procedure. These new summary tables will only include information from Sites 1 and 3 since 24 hour data are not available from Site 2.

The individual tables repeated for the 24 hour safety analysis can be found in the Table of Contents in Appendix 1.

An update was made to the definition of treatment emergent. In this retrospective study, it was originally assumed that all adverse events entered were treatment emergent. Given the updates to the adverse event data collection, subjects with multiple procedures may have events repeated across subsequent procedures. In cases where the onset date is clearly prior to the procedure (ie, onset date < procedure date), these events will not be considered treatment emergent.

While additional safety data will be collected with respect to laboratory data through 24 hours, no summarization is planned. All 24 hour lab data will be listed.

A summary table of patients receiving blood products transfused will be provided by product and timepoint.

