## 13.0 OUTCOME MEASURES

1. Percent decrease in WBC count in patient blood following apheresis procedure. Calculation:  $(WBC_{pre} - WBC_{post}) / WBC_{pre} \times 100\%$ .
2. Percent of processed WBC which are removed, i.e. Collection efficiency for WBC achieved by Spectra Optia system. Calculation:  $(WBC/\mu L \text{ depletion product} \times \text{depletion product volume}) / (WBC_{pre} + WBC_{post}) / 2 \times \text{total processed blood volume}$ . Note, the literature refers to this calculation as CE1 (%) [13].
3. Adverse events (AEs) during the WBCD apheresis procedure and for 2 hours post-procedure.

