## AMENDMENT 1.0 SUMMARY OF CHANGES

Protocol Title:	Multicenter, Retrospective Data Collection of Routine Clinical Use with the Spectra Optia® Apheresis System for White Blood Cell Depletion
Protocol Number:	CTS-5043
Version/Date:	Original version 1.0/18 Feb 2014 Amendment 1.0/28 Sep 2016
Rationale:	This amendment adds to the protocol original version 1.0, dated 18 February 2014.  This amendment was made to address regulatory agency feedback and to extend the duration of safety data collection following the apheresis procedure.
Changes from Original Version 1.0:	Previously during this retrospective study, safety data were collected during the White Blood Cell Depletion (WBCD) apheresis procedure and for up 2 hours post-procedure.  With this amendment, safety data (eg, adverse events [AE], blood product transfusions, and clinical laboratory results, as available) will be collected for the 24-hour time period following the WBCD procedure. No other changes are made to study conduct, subject enrollment, or data analysis.

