## SYNOPSIS

Protocol Title:	Multicenter, Retrospective Data Collection of Routine Clinical Use with the Spectra Optia® Apheresis System for White Blood Cell Depletion
Protocol Number:	CTS-5043
Target Population:	Patients who have undergone WBCD via the Spectra Optia Apheresis System which is likely to include patients with severe leukocytosis in acute leukemia (acute myeloid leukemia [AML], acute lymphoblastic leukemia [ALL], or in chronic myeloid leukemia [CML]) or to prevent tumor lysis syndrome.
Device Description:	The Spectra Optia System for WBCD is comprised of (1) hardware (the actual apheresis machine) and a removable centrifuge filler (2) a sterile single-use disposable tubing set (the Spectra Optia IDL set) and (3) embedded software V7.2 or higher for WBCD.
Intended Use:	The Spectra Optia Apheresis System, a blood component separator, is intended for use in therapeutic apheresis and cell collections and may be used to perform WBCD.
Objective:	To gather a broader knowledge and information from routine clinical use on the performance and safety of WBCD via the Spectra Optia Apheresis System.
Outcome Measures:	

Percent decrease in white blood cell (WBC) count in patient blood following apheresis procedure.

Percent of processed WBC which are collected, i.e. Collection efficiency for WBC achieved by Spectra Optia.

Adverse events during the WBCD apheresis procedure and for up 24 hours post-procedure.

Inclusion Criteria:	Patients having received a minimum of 1 WBCD procedure via the Spectra Optia Apheresis System.
Protocol Design:	This is a multicenter, retrospective data collection to evaluate the in routine use performance and safety of WBCD performed via the Spectra Optia Apheresis System.
Data Collection Duration:	Routine use data will be collected retrospectively from November 2011 to December 2013.
Statistical Methodology:	Patient demographics and performance parameters will be summarized with the mean, standard deviation, median, and range for continuous variables and with frequencies and percentages for discrete variables.

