### 1.1 Rationale for Amendment 1.0

The protocol original version 1.0 (dated 18 Feb 2014) was conducted and the device performance and safety data were summarized, including retrospective safety data for 2 hours following the apheresis procedure. Upon consideration of study results by the US Food and Drug Administration, regulators requested retrospective safety data not just for the 2 hours following the apheresis procedure, but also for the full 24 hours following the apheresis procedure.

This amendment was made to address regulatory agency feedback and to extend the duration of safety data collection following the apheresis procedure. With this amendment, safety data (eg, adverse events [AEs], blood product transfusions, and clinical laboratory results, as available) will be collected for the full 24-hour time period following the WBCD procedure, as requested by the US Food and Drug Administration. Under protocol version 1.0 (dated 18 Feb 2014), safety data were collected for the first 2 hours following apheresis; this amendment will collect safety data in the 22-hour time period from 2 hours postapheresis until 24 hours postapheresis.

This protocol amendment does not make changes to any of the following topics defined in the protocol original version (dated 18 Feb 2014): the study population, the definition of AEs and serious adverse events (SAEs), AE characterizations (eg, severity, action taken, relationship, outcome, SAE criteria), data analysis, or study management procedures.

This amendment does collect the following new information:

- Collection of AEs in the 22-hour time period from 2 hours postapheresis until 24 hours postapheresis
- Additional characterization of AE relationship to underlying disease or treatment for underlying disease (eg, chemotherapy)
- Reason for transfusion of blood products, if transfusions were administered in the 24-hour period postapheresis
- Postapheresis clinical laboratory results, as available

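### The SAP's overall 2-hour and 24-hour adverse event columns rest on different sites, and no listed table isolates 2–24 hours, the period Amendment 1.0 was written to add

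*SAP*

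**What the plan says.** **The outcome.** Section 13.0 of the 2014 protocol defines the safety outcome as "Adverse events (AEs) during the WBCD apheresis procedure and for 2 hours post-procedure". The synopsis of Amendment 1.0 replaces this with "Adverse events during the WBCD apheresis procedure and for up 24 hours post-procedure". Section 1.1 of the amendment gives the reason: having considered the 2-hour results, the US regulator asked for safety data not only for 2 hours "but also for the full 24 hours following the apheresis procedure". The same section describes the new collection: "this amendment will collect safety data in the 22-hour time period from 2 hours postapheresis until 24 hours postapheresis".

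**The analysis, according to the amendment.** Its summary of changes says "No other changes are made to study conduct, subject enrollment, or data analysis", and Section 1.1 also lists data analysis among the topics left unchanged.

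**The analysis, according to the SAP addendum.** Section 4 says "The initial set of safety summary tables will remain as the core safety analysis", covering the start of the procedure to 2 hours after it. Further tables will "summarize (cumulative) adverse events from the start of the procedure through 24 hours post procedure". On sites it says: "These new summary tables will only include information from Sites 1 and 3 since 24 hour data are not available from Site 2". Section 2 says Site 2 is not part of the additional collection, but that its data are carried into the new database.

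**The table list.** Appendix 1 gives eight adverse event tables in paired 2-hour and 24-hour versions, plus one (events leading to discontinuation of study procedures) at 2 hours only. All carry the label Safety Analysis Set with a monitoring window. No title mentions a site restriction, and none names a 2–24 h window.

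**The concern.** The amendment exists to show what happens between 2 and 24 hours. The natural way to read that from the listed tables is to set the overall 2-hour column beside the overall 24-hour column. If the first includes Site 2 and the second does not, the difference reflects both the extra 22 hours and the removal of a site. The table titles would not warn the reader.

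There is some reason not to treat Site 2 as interchangeable with the others. SAP Section 1.1 says that hydroxyethyl starch was used for most procedures at Site 3 and nowhere else, and blood warmers only at Site 1. Site 2 is thus the one site that used neither. This does not show that its adverse event rate differs, but equality cannot be taken for granted.

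There is also a mismatch of status. The amended outcome runs to 24 hours, while the SAP gives the word core to the 2-hour tables and does not say which tables analyse the amended outcome.

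**Working it through.** The plan has no figure to reproduce. The study is descriptive, without hypothesis tests, and the target of at least 20 procedures (protocol Section 8.1) has no calculation behind it. The check is an identity, followed by illustrations with assumed rates.

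**Notation.** Let *A* be the 2-hour rate at Sites 1 and 3, *B* the 24-hour cumulative rate at Sites 1 and 3, *C* the 2-hour rate at Site 2, and *w* Site 2's share of all procedures. The same algebra holds per patient if *w* is the share of patients.

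**Identity.**

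- Overall 2-hour column, all sites: (1 − *w*)*A* + *wC*
- Overall 24-hour column, Sites 1 and 3: *B*
- Apparent change = *B* − (1 − *w*)*A* − *wC* = (*B* − *A*) + *w*(*A* − *C*)

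The first term is the true increment at Sites 1 and 3. The second is the distortion. It is zero when *A* = *C* and can take either sign.

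**Illustration 1: 20 procedures, assumed 14 at Sites 1 and 3 and 6 at Site 2.** At Sites 1 and 3, 4/14 have an event by 2 hours and two more have a first event by 24 hours. The true increment is 6/14 − 4/14 = 2/14 = +14.3 points.

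- Site 2 with 5/6 at 2 hours: overall 9/20 = 45.0% against 6/14 = 42.9%, an apparent change of −2.1 points.
- Site 2 with 0/6 at 2 hours: overall 4/20 = 20.0% against 42.9%, an apparent change of +22.9 points.

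The identity agrees: 14.3 + 0.3 × (28.6 − 83.3) = −2.1, and 14.3 + 0.3 × (28.6 − 0) = +22.9.

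**Illustration 2: a milder contrast, assumed 10 procedures per site.** At 2 hours 3/20 at Sites 1 and 3 and 3/10 at Site 2 have an event, so 6/30 = 20% overall. One more procedure at Sites 1 and 3 has a first event by 24 hours, giving 4/20 = 20%. The overall columns show no change, while Sites 1 and 3 rose from 15% to 20%.

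**Range.** Apparent change in points when the true increment is assumed to be 15 points:

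| 2 h rate, Sites 1+3 / Site 2 | *w* = 10% | 20% | 33% | 50% |
|---|---|---|---|---|
| 40% / 40% | 15 | 15 | 15 | 15 |
| 40% / 20% | 17 | 19 | 21.7 | 25 |
| 40% / 60% | 13 | 11 | 8.3 | 5 |
| 50% / 10% | 19 | 23 | 28.3 | 35 |
| 10% / 50% | 11 | 7 | 1.7 | −5 |

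A negative entry is impossible for a cumulative measure on one site set, so it can only come from the change of sites.

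**After the fix.** With both windows on Sites 1 and 3, the distortion term disappears. Illustration 1 gives +14.3 points whatever happened at Site 2.

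**The case against.** A reader might go further and infer that the added risk after 2 hours cannot be read from the planned output at all. The documents do not support that:

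- SAP Section 1.1 says existing presentations already inform on starch use (Site 3 only) and blood warmers (Site 1 only). That makes sense only if results are shown by site. If the 2-hour adverse event tables follow that layout, adding the Site 1 and Site 3 columns gives the matching figure, because each patient belongs to one site.
- Section 2.4 of the amendment collects event start times, and Listing 16.2.3.1 lists adverse events. In a study this small the split might be rebuilt by hand.
- Appendix 1 gives titles only. The table shells and SAP Version 1.0 are not among the documents, so a suitable column cannot be ruled out. The inclusion of Site 2 in the 2-hour tables is itself an inference from SAP Sections 2 and 4.

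A second strong inference would be that the SAP demotes the amended outcome, and that the all-site 2-hour tables should become merely supportive. Against this, no test or success criterion hangs on the word core, eight of the nine adverse event tables appear at both windows, and the amendment itself says that data analysis is unchanged. The 2-hour window is also the only one with data from every site, which is a fair reason to keep it prominent.

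These points remove the claim of unreadability and the case for demotion. They do not supply a listed table for 2–24 hours or a listed 2-hour table on Sites 1 and 3, and site columns are only inferred. The answer to a regulator's specific question should not depend on reconstruction from a listing. Nor does unchanged analysis settle which tables go with the outcome: summarising the stated outcome descriptively, as before, now gives a 24-hour summary.

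**Conclusion.** The point holds in limited form. The amended outcome runs to 24 hours, the SAP's core tables stop at 2 hours, and the listed tables leave the overall columns of the two windows not directly comparable. The error in a direct comparison is *w*(*A* − *C*): none if Site 2's 2-hour rate matches that of Sites 1 and 3, and otherwise in either direction. Over the assumed range of shares (10% to 50%), a 20-point rate gap shifts the result by 2 to 10 points and a 40-point gap by 4 to 20 points. An apparent fall needs a large contrast, as with 5/6 at Site 2 in the first illustration, but the second shows a real rise hidden by a moderate one.

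The conclusion assumes that the 2-hour tables pool all three sites and that readers compare overall columns. Every site share and rate used is an assumption. The flaw lies in presentation and labelling. The data needed to answer the question are due to be collected.

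**What to change.** 1. In each 24-hour adverse event table, show three columns on the same Sites 1 and 3 denominator: start to 2 h, new onset in 2–24 h, and cumulative to 24 h. State that a patient or procedure with events in both windows counts in both of the first two columns, so these need not add up to the third.
2. Put the sites and denominator in the title of every 2-hour and 24-hour adverse event table.
3. State in SAP Section 4 that the 24-hour tables analyse the safety outcome as amended, and keep the all-site 2-hour tables alongside them. Align the amendment's statement that data analysis is unchanged.
4. Say how events with a start date but no usable start time are assigned to a window, for example in a separate row, since these are retrospective records.

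The cost is SAP wording and two extra columns. Event start times (amendment Section 2.4) and procedure stop times (SAP Section 5) are already being captured, so no new data are needed.
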